3.2.9 Final stakeholder workshop

We will run a final workshop involving collaborators, stakeholders, our PPI group and the research team to finalise the intervention, explore perspectives on factors that influence scalability and sustainability of the intervention, including all potential costs from multiple perspectives, and prioritise outcomes for future feasibility and evaluation research. With permission from workshop participants, the workshop will be recorded. Afterwards we will take notes on any recommendations to inform future intervention development and evaluation.

4 Data Management

4.1 Personal Data and Data Collection

Personal characteristics data will be used only to describe the population sample and will not be linked to focus group/interview data. Data will be reported at a group rather than individual level (e.g., mean age, frequency of gender, relationship to deceased, etc). To link data from pre intervention to post intervention, each participant will be given a unique study ID code. Because follow up data will be gathered with the support of the research team, participants can be prompted if they do not recall their unique study ID code.

Quantitative study data will be gathered via JISC surveys, a University of Edinburgh supported survey platform that uses secure encryption and storage of data. Survey data will be downloaded directly to University of Edinburgh managed Microsoft Office 365 Teams space (see 4.2 below). Qualitative data in the form of interview and focus group notes and auto transcripts will be generated by Microsoft Teams and downloaded to the secure Microsoft Teams space, where they will be de-identified before any further processing. There will be minimal need for transport or transfer of field notes, as all data capture will occur within Microsoft Teams. The exception is if a participant requests a telephone interview. In these circumstances, the researcher conducting the interview will take notes and then transfer these to an electronic file, for processing and storage within the secure Microsoft Teams space. Once notes are digitised in this way, any original hand written notes will be securely shredded.

4.2 Storage of Data

The research team use a secure and encrypted University of Edinburgh managed Office 365 (Microsoft Teams, SharePoint and OneDrive) space for everyday storage and processing of study materials. This has controlled access. Data will be kept within private channels within that team, and access to specific folders will be managed according to need. Personal data, used for study administration such as contacting participants for post intervention data, will be kept securely within these restricted channels and will be securely deleted at the end of the study (January 2025).

Once the study is complete, longer-term archiving of the anonymised research data will use the Edinburgh Data store, which is also password protected and encrypted. We do not plan to share data through public repositories such as Edinburgh Data Vault or any other similar data-sharing repository. The anonymised data will be retained for ten years, after which time it will be reviewed as to whether retention or secure deletion is in the public interest.

4.3 Processing of Data

Data will be processed for the purposes of study administration, and for the purposes of answering research questions. Where practical such processing will make use of Office 365 cloud-based storage and not save local copies of files. Temporary copies may be made for specific circumstances such as accessibility of reliable internet, but the files will be securely uploaded to the Microsoft Teams space as soon as practical and local copies secure deleted. All devices being used to access data are password protected.

4.4 External Transfer of Data and Data Controller

The University of Edinburgh remains the data controller, with specific responsibility for this being held by the project joint principle investigators ([name] and [name]) and delegated to project Research Associate ([name]). These core members of the research team have all undertaken Good Clinical Practice in Research, and University of Edinburgh Data Management training. Data will not be transferred to, shared with, supported by or otherwise available to third parties outside the research team. The UoE procedures and data capture are separate from those used by Marie Curie and Cruse Scotland. We have good relationships with our partners; they are clear about who owns the project data (University of Edinburgh) and the uses the data will be put to. We have been clear with collaborators about expectations around ownership, contribution, authorship credit and final use and ownership of the MY Grief, My Way resource and all aspects of that have been discussed and agreed.

The partner organisations (Marie Curie Bereavement Support and Cruse Scotland will pass personal data to the University of Edinburgh with the permission of the potential research participants, in the form of a name and contact details, so that they can be recruited to the study. The University of Edinburgh will inform the partner organisations if a participant consents to undertake the study, for the purpose of triage and intervention by the partner organisation.

Some of our wider project team are employed by different institutions. They may facilitate aspects of analysis of qualitative data transcripts. These will be de-identified before analysis. The project partners all have access to our secure Office 365 space and therefore they will be able to undertake their data analytic tasks within that space, except as described under section 4.3 above. These aspects of data sharing will be explicitly consented by the participant.

Anonymous usage and website feedback data will be gathered by the website itself. The web developer and production company Morrow Communications Ltd will download that data and share with the research team at the University of Edinburgh.

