3.2.4 Intervention content and delivery

We have chosen to name our intervention My Grief My Way following consultation with collaborators, stakeholders, our bereaved persons and Marie Curie Voices PPI groups. Based on the programme theory logic model and data gathered in Phase 1, the research team will determine specific techniques and materials to use in the intervention, and the format this will take (e.g. style, format, timing, order, emphasis, exercises used, type of materials, accessibility, opportunities for user discussion etc.). Materials will include videos, interviews with people about their experience of grieving, readings, poetry, artwork, animation, and audio exercises created and curated for the project such as:

- Stories relating to grief experiences that illustrate common sticking points in grieving.
- Stories that illustrate how the ACT skills of 'be present', 'open up' and 'do what matters', can support grieving, shared via video, audio files and images.
- Metaphors relating to the experience of grief presented via audio and video files
- Exercises which can be completed online or downloaded by the bereaved person
- Mindfulness and similar exercises, delivered via audio files
- Links to psychoeducational resources linked with coping with grief, and other therapeutic approaches including compassion focused therapy and trauma therapy.

• Signposting for bereaved people who feel they need additional support to that offered via the online resources.

We are working with Morrow Communications, a media production company, to develop these resources and make them available online. Our prototype will be user tested by members of our key stakeholder organisations and bereaved persons PPI group. Usability will be assessed by a heuristic evaluation guided by Nielsen's 10 general principles for user interface design (Appendix 15). Bereaved participants will be able to access the resource in a self-directed manner, or with the support of a bereavement support volunteer who has been trained in ACT.

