3.2.5 Online access to the intervention materials

Our ACT based bereavement support resource will be hosted on the My Grief My Way website (not yet live). Study participants will be provided with the website link. The site will be live so that site usage data can be collected using Google Analytics and will inform intervention development. The landing page will include a disclaimer so in the unlikely event that the site is found by a member of the public, it will be clear to them that it is part of a research study, and who to contact for further information. The disclaimer will describe the nature of the site, will advise people that the tools and techniques are based on evidence based psychological therapy principles, but that use of a self-help website is not a substitute for professional mental health care. The page will signpost people to their primary care physician for further information and support.

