Qualitative research with bereaved participants: Participants will be invited to take part in focus groups or individual semi-structured interviews if preferred. The aim of the focus groups will be to explore their experience of accessing the My Grief My Way resource, and any impacts it might have had on them, as well as giving us feedback about the materials. We will hold 2 to 3 focus groups after each cycle, depending on participant availability. Semi-structured interviews will be conducted where a participant cannot or prefers not to take part in a focus group. See topic Guide in Appendix 17. Focus groups/interviews will be conducted at a mutually agreed time via Microsoft Teams (or by telephone if preferred). These will be audio recorded, transcribed, and anonymised by a member of the research team. Data will be analysed using rapid qualitative analysis techniques²⁸ informed by a framework approach and results following each cycle will feed into intervention delivery for the subsequent cycle.

Intervention module usefulness: Bereaved participants' perspectives on intervention module usefulness (n = 30-45): This will be accessed by participants via a feedback icon on each module webpage. By clicking on the icon, participants will be asked an open question on the usefulness of the module they have completed. Data will be imported into NVivo and analysed thematically following each cycle, and the findings will be used to refine the intervention prior to subsequent iterations.

Intervention engagement will be assessed via routine website activity collected via Google Analytics. This will include the times each webpage was accessed, amount of time on each webpage, downloads of materials from the website etc. We will analyse this data after each research cycle to assess the relative usage of different intervention components, and estimate levels of engagement.

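### Website usage and module feedback are anonymous and come from one shared live site, so they cannot be analysed by participant, mode or level of need, and no step is described to exclude other visitors

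*Protocol*

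**What the plan says.** **Engagement.** Section 3.2.8 of the protocol states: "Intervention engagement will be assessed via routine website activity collected via Google Analytics". The data are analysed after each cycle "to assess the relative usage of different intervention components, and estimate levels of engagement".

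**Module feedback.** The same section describes bereaved participants' "perspectives on intervention module usefulness (n = 30-45"). The route is one open question, "accessed by participants via a feedback icon on each module webpage".

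**Nature of the data.** Section 4.4 states: "Anonymous usage and website feedback data will be gathered by the website itself". The web developer downloads these data and passes them to the research team.

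**Access.** Section 3.2.5 states: "The site will be live so that site usage data can be collected using Google Analytics and will inform intervention development". Study participants receive the link, and a landing-page disclaimer covers any member of the public who comes across the site. No log-in, individual link or traffic filter is described. Section 3.2.6 sends self-directed and facilitated participants to the same website.

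**Study ID.** Sections 3.2.8 and 4.1 describe the unique identifier only as the means of joining pre- and post-intervention data.

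**Other possible users.** Section 3.2.4 states: "Our prototype will be user tested by members of our key stakeholder organisations and bereaved persons PPI group". It does not say whether this takes place on the live site or during a cycle.

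**The concern.** Anonymity is a choice made when the data are collected. If no participant, mode or cycle marker is recorded, no later analysis plan can restore it. Three uses of the web data are affected.

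- **Level of engagement.** The number of participants who never opened the site, or the number of modules each one used, cannot be obtained. Pre-post changes in the outcome measures then cannot be read against exposure: someone who never visited looks the same as someone who used every module.
- **Comparison of modes and needs.** The intervention is delivered in two modes, and research question 2a asks whether acceptability differs by level of need. The web data can contribute to neither comparison.
- **Module feedback.** The label gives a number of people, while the method yields a number of anonymous comments.

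There is also no described means of telling a bereaved participant's visit from anyone else's. With 10-15 participants per cycle, modest use by others could alter the pattern of component usage, if it occurs.

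**Working it through.** **1. The protocol's own figure.** Section 3.2.1 gives three cycles and section 3.2.2 gives 10-15 bereaved participants per cycle. 3 × 10 = 30 and 3 × 15 = 45. The 30-45 attached to module feedback is therefore the full recruitment target, not an expected number of respondents.

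**2. What the feedback can show.** Leaving a comment requires clicking an icon, so it is optional, and it can be done on every module page. If C anonymous comments arrive, the number of distinct authors can be anything from 1 to C. For illustration, 30 comments fit 30 people commenting once each (30 × 1) and also 10 people commenting three times each (10 × 3). Nothing collected separates the two, or shows that every author was a bereaved participant.

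**3. What the usage data can be split by.**

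| Split | Marker needed | Described in the protocol? |
|---|---|---|
| Participant | Study ID on web data | No; the ID is described for pre and post data only (3.2.8, 4.1), and web data are anonymous (4.4) |
| Mode | Mode-specific link or code | No; both modes use the same website (3.2.6) |
| Level of need | ID joined to baseline data | No; ruled out by anonymity (4.4) |
| Cycle | Dates | Partly; analysis follows each cycle, so dates can serve if cycles do not overlap |
| Participant or other visitor | Separate link or filter | None described |

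Dates cannot stand in for mode. Section 3.2.1 allows both ways of working within each cycle, and section 3.2.7 lets a participant move from self-directed to facilitated use.

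**4. What remains possible.** Page counts, time on page and downloads still give the relative usage of components across all visitors together. That part of the stated purpose can be met, provided visits by others are few or are removed.

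**5. Who else might visit.** About 20 volunteers and staff are to be trained (3.2.2), including a session on supporting people with the resource (3.2.3). After each cycle volunteers are asked how the resource could be improved (3.2.8). The nine-member public-involvement group comments on content (3.1.1) and tests the prototype (3.2.4). These passages make such visits plausible. None of them states that the visits take place on the live site during a cycle.

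**The case against.** The strongest reply is that the protocol promises little from these data. It speaks of relative component usage and levels of engagement, and nowhere of web engagement per participant, by mode or by need. Question 2a concerns acceptability, for which focus groups, interviews and linked questionnaires are the main sources. Qualitative findings are explicitly what feeds each next cycle; website activity is supplementary. The 30-45 can be read as the number invited to comment on one open question analysed thematically, with no response rate claimed. Anonymity is defensible in a small bereavement study, particularly where an outside company downloads the data.

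Most of this stands, and it limits the point to the web data. It does not remove the point. An estimated level of engagement needs a known set of users, and a figure labelled n should not be left for the reader to take as respondents.

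A reader might go further and infer that most recorded visits come from non-participants, because about 20 volunteers and staff plus 9 public-involvement members make 29 people against 10-15 participants per cycle. The documents do not support this. The share is 29r/(29r + participants), where r is visits per other person relative to a participant, and the protocol gives no r:

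- r = 0 gives 0%.
- r = 0.1 gives 2.9/17.9 = 16% to 2.9/12.9 = 22%.
- r = 1 gives 29/44 = 66% to 29/39 = 74%.

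The last line requires all 29 to use the site as much as a participant in every cycle. Yet testing may precede the cycles and could then be cut off by date, and trained volunteers may decide not to provide support. Section 3.2.5 names study participants as recipients of the link; since section 3.2.8 counts volunteers as a participant group too, that sentence does not settle whether volunteers receive it. No mixing at all is compatible with the text, so no percentage should be quoted.

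A reader might also call the site open to all. The protocol says it is live and describes no access control, which is less than saying that there is none.

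**Conclusion.** The point holds for attribution. As written, none of the usage or module-feedback data from any of the three cycles can be assigned to a participant, a mode or a level of need, and no step is described to exclude visits by others. This follows from sections 3.2.5, 3.2.6, 3.2.8, 4.1 and 4.4 read together and needs no assumption about visitor behaviour. It rests on one reading: that the website feedback called anonymous in section 4.4 includes the module comments.

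The label n = 30-45 overstates what the feedback route can show, since it equals the recruitment target and not a count of commenters.

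The size of any mixing is unknown and could be zero. The study is not invalidated: acceptability can still be studied through questionnaires, focus groups and interviews. The change is worth making before launch because a marker that was not collected cannot be added afterwards.

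**What to change.** **Minimum change, data remain anonymous**
- Give bereaved participants links tagged by cycle and initial mode (self-directed or facilitated).
- Give any volunteers, public-involvement members, staff or testers who use the site a separate tagged link, and exclude that traffic from the engagement analysis. Count visits arriving without a tag separately.
- In section 3.2.8, restate module feedback as the number of comments received from up to 30-45 invited participants.
- State that engagement is reported in aggregate, by cycle and initial mode.

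The cost is a small developer task and a few lines of text. Two limits remain. A tag for initial mode will not reflect a later switch under section 3.2.7. Nor is mode a measure of need, because at Marie Curie it depends on which service the person called.

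**If per-participant engagement is wanted** (for example, the number who never opened the site)
- Use a pseudonymous study code on the web data, and amend section 4.4 and the consent form to match.

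This costs more. Usage data become pseudonymised personal data handled by the web developer, and section 4.4 also says that data will not be available to third parties outside the research team, so the data-flow text would need revising. Access gains an extra step if the code has to be entered. If the sponsor judges that cost too high, the minimum change is sufficient.

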4.5 Data Breaches

If a potential breach is identified by the research team, the sponsor will be notified within 24 hours. The sponsor will assess the impact of the breach on the scientific value of the trial, to determine whether the incident constitutes a serious breach and report to research ethics committees as necessary.

5 Risks

It is possible that some participants may be upset by thinking and talking about their grief and the impact this has on their wellbeing. However, they will have standard care support from Marie Curie and Cruse Scotland support services to address any concerns they may have during the study. Participants will be monitored carefully so that any change in their condition including deteriorating wellbeing is identified and addressed. This will include proactive checks made by Marie Curie and Cruse staff as part of routine monitoring and care.

The My Grief My Way website will also have clear contact details so that if any participant feels that the material has had a detrimental effect on them, they can contact us. If that occurs, the participant's concerns will be investigated through a phone call with Joint PI [name], who is a Chartered Clinical Psychologist, with experience of supporting people in distress. During that telephone conversation the issue will be identified, the participant offered choices to remain in the study or to exit, and help will be given to find alternative sources of support, such as a higher level of support from our partner organisations, or through NHS services such as general practitioner. Given that MGMW is aimed at people with moderate bereavement needs, it is unlikely that any such adverse events would necessitate an emergency response, but the website itself will contain clear links to UK based emergency supports, such as NHS24 and The Samaritans.

6 Oversight Arrangements

6.1 Inspection of records

Investigators and institutions involved in the study will permit study related monitoring and audits on behalf of the sponsor. In the event of audit or monitoring, the co-PIs agree to allow the representatives of the sponsor direct access to all study records and source documentation. In the event of regulatory inspection, the Investigator agrees to allow inspectors direct access to all study records and source documentation.

6.2 Study monitoring and audit

The Sponsor Representative will assess the study to determine if an independent risk assessment is required. If required, the independent risk assessment will be carried out by the ACCORD Quality Assurance Group to determine if an audit should be performed before/during/after the study and, if so, at what frequency.

7.3 Study oversight

The study has a wider stakeholder group comprised of the research team, plus representatives of the partner organisations and PPI representatives. These are listed on Page 1 of this protocol. The stakeholder group meets on a monthly basis and the PI's report on progress and plans. Minutes are kept of these meetings and circulated. This formal meeting provides transparent oversight of study management.

7 Good Clinical Practice

7.1 Ethical conduct

The study will be conducted in accordance with the principles of the International Conference on Harmonisation Tripartite Guideline for Good Clinical Practice (ICH GCP).⁽³⁶⁾ Before the study can commence, all required approvals will be obtained and any conditions of approvals will be met.

8 Investigator Responsibilities

The co-PIs (AF/DG) are responsible for the overall conduct of the study and compliance with the protocol and any protocol amendments. In accordance with the principles of ICH GCP, the following areas listed in this section are also the responsibility of the co-PIs. Responsibilities may be delegated to an appropriately qualified member of study staff.

